determine the subject's HRQOL.¹¹¹ The HUI is a generic, utility-based HRQOL instrument applied in patients with a wide range of medical conditions.^{111,112} It has eight attributes: Vision, hearing, speech, ambulation, dexterity, emotion, cognition and pain. The individual health domain scores range from 0.00 (maximum impairment) to 1.00 (no impairment) and the multi-attribute (HUI index) scores, a multiplicative function of individual attribute levels, range from 0.36 to 1.00 with anchors 0.00 = dead and 1.00 = perfect health. Naglie et al found that test-retest reliability exceeded the standard for adequate reliability of 0.70 in those with mild dementia (ICC = 0.75).¹¹³ [name] recently published a paper that provides new evidence regarding the construct validity (including responsiveness) of the HUI in community-based subjects with dementia.¹¹² The mean HUI multi-attribute utility score for 408 primary care patients with dementia was 0.54 (SD = 0.23) and the mean one year change was -0.30 among 240 dementia patients who remained in their own home after one year of receiving dementia care program whereas the mean one year change was -0.76 among 29 dementia patients who moved into a skilled nursing home facility.¹¹²

Mood and Anxiety Outcomes

We will use the **Patient Health Questionnaire–9 (PHQ-9)**¹¹⁴⁻¹¹⁶ and **Generalized Anxiety Disorder Scale (GAD-7)**^{117,118} to determine the impact of screening on our subjects' mood and anxiety at baseline, 1,6, and 12 months. We have used both instruments in various primary care-based research studies including our dementia collaborative care trial.^{34,51,93,114-118} The PHQ-9 is a nine-item depression scale with a total score from 0 to 27 and the GAD-7 is a seven-item anxiety scale with a total score from 0 to 21. Both of these scales are derived from the Patient Health Questionnaire; have good internal consistency and test–retest reliability; as well as convergent, construct, criterion, procedural and factorial validity for the diagnosis of major depression and general anxiety disorder.¹¹⁴⁻¹¹⁸ In our previous primary care studies, the mean

PHQ-9 scores ranged from 3.8 (SD = 5.1) to 4.4 (SD = 5.6) and the mean GAD scores ranged from 2.7 (SD = 3.2) to 3.2 (SD= 3.5).^{34,114-118}

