The outcome measures for this study are HRQOL (HUI multi-attribute utility score), mood (PHQ-9) and anxiety levels (GAD-7) obtained at baseline, 1, 6, and 12 months. To verify the comparability of the randomized groups, patients' baseline characteristics between the screened and no screening groups will be compared using *t*-tests for continuous variables and chi-square tests for categorical variables. We will carefully examine the distributions of continuous variable and use alternative approaches such as transformation or nonparametric methods in cases of violation to the normal distribution assumption. We will also examine the frequency distribution of all categorical variables and adopt exact inference procedures in cases of zero or small cell size. We will compare the baseline characteristics between subjects with missing outcomes due to death or refusal at 12 months to subjects who completed the follow-up

to detect potential violation to the missing at random assumption. Further sensitivity analyses will be performed using various methods of imputation or a full parametric likelihood approach assuming various patterns of missing data.¹²²

Primary Aim tests the hypothesis that subjects in the dementia screening group will have higher health-related quality of life compared those in the no screening group. We will compare mean measures of health-related quality of life levels in the “screening” group to the “no screening” group using analysis of covariance (ANCOVA) while including baseline measures as covariates. We will first conduct the ANCOVA models separately for outcomes obtained at 12 months while adjusting for baseline measures. We will then use the mixed effect models to examine whether the difference between the two groups changes over time using repeated HUI measures as the dependent variables, group, time, interaction between group and time as independent variables while controlling for other baseline covariates. All analyses will be conducted using SAS 9.3 (SAS Institute, Carey, North Carolina). For the patients who do not complete the 12 month surveys for health-related quality of life, they will be excluded from the analyses followed by sensitivity analyses on missing data described below.

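### The primary 12-month HUI analysis uses completers only and drops deaths with refusals, and the baseline comparison offered as a check on missing at random cannot test that assumption

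*Combined protocol and SAP*

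**What the plan says.** All of this is in section I, Statistical Plan, of the combined protocol and SAP, unless noted.

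- The first analysis for the Primary Aim is an ANCOVA of 12-month HUI adjusted for baseline. Of patients without the 12-month survey it says "they will be excluded from the analyses followed by sensitivity analyses on missing data described below". No text on missing HUI follows; the only description comes earlier in the section.
- The plan compares baseline characteristics of "subjects with missing outcomes due to death or refusal at 12 months" with those of completers. The stated purpose is "to detect potential violation to the missing at random assumption".
- It then adds: "Further sensitivity analyses will be performed using various methods of imputation or a full parametric likelihood approach assuming various patterns of missing data". It names no method, no value for a death and no range of departure.
- A repeated-measures model follows: "We will then use the mixed effect models to examine whether the difference between the two groups changes over time". Its terms are "group, time, interaction between group and time as independent variables while controlling for other baseline covariates". No 12-month contrast is named, and the role of baseline HUI is not stated.
- Section H, Data Collection, describes the HUI index "with anchors 0.00 = dead and 1.00 = perfect health". The analysis plan never applies the value for dead.
- The power paragraph allows 10% missing at 12 months, without a split by arm or by cause.

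**The concern.** Two separate things are wrong.

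First, the primary contrast discards information already collected. A patient seen at 1 and 6 months and then lost contributes nothing to the ANCOVA. If later loss follows a poor 6-month HUI, and does so differently in the two arms, the completer contrast is biased although the data needed to correct it are in hand. Deaths are treated as if they were refusals, on a scale that defines a value for death.

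Second, the diagnostic is misdescribed. Missing at random concerns dependence on unseen values given the observed ones, and observed baseline data cannot test that. A difference in baseline characteristics shows only that data are not missing completely at random. A reader could take a clean comparison as support for the completer result, or a significant one as evidence against a baseline-adjusted ANCOVA that is in fact unbiased.

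This matters here because the effect sought is small, 0.094 SD, so modest biases are not negligible beside it.

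**Working it through.** **1. The plan's own figure.** Inputs from the power paragraph: effect 0.094 SD, 80% power, two-sided alpha 0.05, 10% missing. Per arm, n = 2 × (1.96 + 0.842)² / 0.094² ≈ 1,777, so 3,554 in total; 3,554 / 0.90 = 3,949, against the stated 3,951. The figure is reproduced. The 10% allowance only enlarges enrolment. It restores precision and does nothing about bias.

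**2. What the baseline comparison detects.** Simulation: 4,000 patients, about 9% missing, true effect 0.094 SD, 300 runs, assumed mechanisms.

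| Mechanism | Baseline comparison significant | Bias of baseline-adjusted ANCOVA |
|---|---|---|
| Loss depends on baseline only (missing at random holds) | 100% of runs | -0.001 SD |
| Loss depends on unseen outcome, screened arm only (missing at random fails) | 5% of runs, the chance rate | +0.051 SD |

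The check signals where there is no bias and is silent where there is. The second row is a deliberately extreme case, used only to show what the check misses. It is not an estimate of bias in this trial.

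**3. Size of the completer bias.** The documents give no loss by arm and no visit correlations, so everything here is assumed: no true effect; correlations of 0.60-0.75 between visits; log-odds of loss rising 0.5-1.5 per SD of worse HUI; 1,000,000 subjects per arm; bias taken against the full-data ANCOVA; Monte Carlo error about 0.0005 SD. The likelihood model uses all visits and adjusts for baseline HUI.

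| Loss depends on | Loss by arm | Completer bias (SD) | Likelihood bias (SD) |
|---|---|---|---|
| Observed 6-month HUI, equal slopes | 10% v 10% | within 0.001 | within 0.001 |
| Baseline HUI only | 12% v 8% | within 0.001 | within 0.001 |
| Observed 6-month HUI, exchangeable correlations | 12% v 8% | 0.004-0.011 | within 0.001 |
| Observed 6-month HUI, correlations decaying from 0.75 to 0.60 | 12% v 8% | up to about 0.017 | within 0.001 |
| Unseen 12-month HUI | 12% v 8% | about 0.008-0.030 | about 0.006-0.025 |

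Against the design effect: 0.017 / 0.094 = 18% where the likelihood model works, and 0.030 / 0.094 = 32% in the last row, where it removes little. The sign depends on which arm loses more.

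**4. Tipping points.** With 1,800 completers per arm, the unadjusted SE is √(2/1800) = 0.0333 SD. Adjusting for a baseline correlated r with the outcome multiplies it by √(1 - r²). If missing screened patients are δ SD worse than assumed and missing controls are as assumed, the estimate falls by 0.10 × δ. Significance is lost at

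δ = (observed effect - 1.96 × 0.0333 × √(1 - r²)) / 0.10.

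- Observed 0.094 SD: (0.094 - 0.0523)/0.10 = 0.42 at r = 0.60; 0.47 at r = 0.70; (0.094 - 0.0432)/0.10 = 0.51 at r = 0.75.
- Observed 0.110 SD, the largest effect in the plan's power table: (0.110 - 0.0523)/0.10 = 0.58; 0.63; (0.110 - 0.0432)/0.10 = 0.67.

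**5. Deaths.** The only HUI mean and SD given are for dementia patients, 0.54 and 0.23 (section H). Scored at 0.00, each percentage point of mortality difference between arms moves the contrast by 0.01 × 0.54 / 0.23 = 0.023 SD, or 0.01 × 0.80 / 0.23 = 0.035 SD if the trial mean were 0.80 (assumed). The documents give no mortality rate, and section J, Limitations, regards one year as too short for mortality outcomes. This is a scaling, not a forecast.

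**The case against.** The plan does not ignore missing data. It commits to a repeated-HUI mixed model and to imputation or full-likelihood sensitivity analyses under various missing-data patterns, wording that may include models outside missing at random. Those analyses do not depend on the baseline comparison; they are to be performed in any case. This stands, and it limits the practical harm of the wrong wording. But the mixed model is planned to examine change over time, it is unclear whether the exclusion sentence covers it too, and the sensitivity analyses are not named.

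The bias is hypothetical. Nothing in the documents shows loss of the HUI survey differing by arm. The 33% refusal rate in the screening section concerns diagnostic assessment, not the survey. The larger values where the fix works need decaying correlations, and the simulations assume that patients once lost do not return. The repair also does least where bias is largest, when loss depends on unseen 12-month HUI. All of this stands.

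The death scaling applies dementia figures to a mostly non-demented cohort. That stands too, and is why scoring deaths belongs among the sensitivity analyses.

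A reader might infer that the planned ANCOVA is imprecise. It is not: it already gains from baseline adjustment. Precision would be lost only in a careless repair.

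**Conclusion.** The concern holds in a limited form. The primary analysis is completers-only with deaths dropped, and the purpose stated for the baseline comparison is wrong, because that comparison cannot test missing at random.

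Under the assumptions shown, the completer bias runs from about zero to about 0.017 SD when loss depends on observed 6-month HUI at 12% v 8%, and nearly all of that is avoidable. It is about 0.008-0.030 SD when loss depends on unseen 12-month HUI, of which a likelihood analysis still leaves about 0.006-0.025 SD.

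A reader might infer that the trial's result will be biased towards screening, or that the primary analysis is invalid. The documents support neither: they give no loss by arm, and so neither the direction nor the size of any bias. The plan should be corrected because the better analysis uses data already being collected, not because harm has been shown.

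**What to change.** 1. Make primary the 12-month group contrast from the planned repeated-measures model, with categorical time, unstructured covariance and all available HUI. Enter baseline HUI as a baseline-by-time covariate, or constrain baseline means to be equal across arms. This detail matters: in simulated trials (12% v 8% loss) the SE was 0.022-0.026 SD with such adjustment, the same as for the ANCOVA, but 0.032-0.033 SD if baseline HUI was left as an unconstrained outcome.
2. Limit the exclusion sentence to a supportive completer ANCOVA.
3. Describe the baseline comparison as descriptive, able to show departure from missing completely at random only.
4. Within the sensitivity analyses already planned, name two:
   - one scoring deaths as HUI 0.00, the anchor stated in section H, with deaths reported by arm;
   - one delta-adjusted imputation, varied separately by arm and extended until the conclusion changes. A cap of 0.6 SD would be too low, since the tipping point reaches 0.67 SD for an observed 0.110 SD.

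Cost: no new data, visits or patients, but it does replace the named primary analysis and adds some analysis work. The primary estimate remains hypothetical with respect to death, and loss that depends on unseen HUI is only partly handled. Scoring deaths as 0.00 also widens the outcome SD: by √((1 - p) + p(1 - p)(0.54/0.23)²), or about 2-10% for an assumed mortality p of 1-5%.

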Primary Specific Aim 2: Test the impact of dementia screening on the mood and anxiety symptoms of patient at baseline and 1, 6, and 12 months (i.e., primary potential harms).

(We hypothesize that screened subjects will not have higher depression or anxiety at one month post-screening (as measured by the Patient Health Questionnaire (PHQ-9) and Generalized Anxiety Disorder (GAD-7) scales)

Secondary Aims: Estimate the cost effectiveness of dementia screening.

(We hypothesize that screened subjects will have an Incremental Cost Effectiveness Ratio (ICER) below the maximum acceptable threshold of \$100,000 per quality adjusted life year saved at 12 months.)

B. Innovation

Pragmatic

Previous studies by our team and others have demonstrated that routine feedback of dementia screening scores, continuing medical education for dementia, and other passive educational interventions can improve rates of diagnosis, but not patient outcomes.^{12,28-32} We have shown that patients and families perceive potential harms from screening and that dementia screening can result in important incremental health care costs.^{21-23,33} Conversely, we and others have also already demonstrated that collaborative care, focused on non-

pharmacologic approaches to behavioral disturbances, can improve patient outcomes under experimental conditions.^{34,35} The innovation of this trial is in moving the process upstream to asymptomatic, older adults, cared for in typical but prepared community-based practices, to document actual benefits and harms, including costs. “Asymptomatic”, in the case of cognitive impairment, is paradoxical in some respects, but we denote asymptomatic to mean that the cognitive impairment is not a presenting symptom of the patient (just as hypertension is asymptomatic but can be detected by screening, cognitive impairment can be detected through screening tests).

Academic Community Partnership

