Secondary Aim 1 compares depression and anxiety levels at 1 month post dementia screening between screened subjects and subjects in the no screening group. ANCOVA models will be used to compare PHQ-9 and GAD-7 obtained at 1 month between the screening and no screening groups adjusting for patients’ characteristics and baseline measures.

Secondary Aim 2 estimates the cost effectiveness of the dementia screening program in comparison to the “no screening”. This economic evaluation will be conducted from the societal and payer perspectives, including the direct medical care costs, caregiver and patient time and transportation costs, and the effect on quality of life for patients and caregivers.¹²³ Costs will be

divided into fixed and variable costs and by the screening, initial assessment phase and the follow-up phase of treatment. Total medical care utilization costs will be estimated for the control and screening groups from healthcare utilization and reimbursement data captured by the Indiana Network for Patient Care (INPC) during the trial. Prescription drug use will also be obtained from the INPC healthcare administrative database. The cost analysis will capture the extent to which screening, early diagnosis and coordinated care of patients with Alzheimer's disease affects medical care costs associated with dementia and co-morbid conditions such as diabetes, made worse by failure to manage dementia. Activity costing will be utilized to estimate the costs necessary to implement and operate the screening and collaborative dementia care management program and the usual care for dementia patients. Patient and caregiver time, staff time, fringe benefits, overhead costs, and materials will be logged by staff using the eMR-ABC software and assessed for the 12 month follow-up period. Included are waiting time, time with patients, time in meetings, lab services, telephone calls and mailings to participants. Excluded are costs associated with research. Transportation costs will be estimated from data on distance from home to clinic. Health care contacts will be dated and checked to avoid double counting via claims and activity costing methods.

Prescription drugs will be valued at the median wholesale price. A dispensing fee will be added for each 100 doses. Unit wage costs and fringe benefits will be standardized applying median values paid to personnel in the region; wage data collected from the health care system partners.

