Statistical Power, derived from sample size estimate, is used to test the primary hypothesis that subjects in the screening group will have higher health related quality of life than the no screening group. Previous randomized trials comparing collaborative care to usual care in demented patients have stated effect size of 0.4 being clinically significant.^{34,35} Considering that the majority of patients in the screening group or the no screening group are not demented, the observable effect size between these two groups will be a combined effect size measure in the non-demented subjects and in those demented subjects receiving the collaborative dementia care program.

Assuming 85% sensitivity of screening instrument and 15% prevalence of dementia in this patient population, to achieve 80% power to detect a significance effect size of 0.094 between the screening group and the no screening group at $\alpha=0.05$ level (two-sided), and allowing 10% of patients with missing follow-up outcomes at 12 months, we need to enroll at least 3951 patients into the study. The effect size of 0.094 between the screening group and the no screening group reflects a difference of 0.40 SD between demented patients in the collaborative dementia care program and demented patients who were not screened and a difference of 0.06 SD in the majority of patients who are not demented in either group. We demonstrate in the table below that our planned sample size of 4,000 will have sufficient power to detect significant differences between the “screen” group and the “no screen” group under various scenarios assuming varying degrees of efficacy measures for the collaborative dementia care program and for the screening only subjects.

Estimated power with a total sample size of 4,000 comparing primary outcome measures between the screening group and the no screening group (two-sided at $\alpha=0.05$) allowing 10% of patients with missing outcomes at 12 months.			
Effect size of collaborative care in demented subjects	Effect size In non-demented subjects	Observable Effect Size	Power Estimate
0.3	0.07	0.091	77.9
	0.08	0.100	85.1
0.4	0.07	0.102	86.4
	0.08	0.110	91.0

For the Secondary Aims, given the sample size of 4000, we will have greater than 95% power to test the equivalence levels in PHQ-9 and GAD-7 at 1 month assuming equivalence differences of 0.6 (SD=5.1) on PHQ-9 and 0.5 (SD=3.2) on GAD-7 based on our previous studies in primary care patients.^{34,51,93,114-118}

J. Limitations

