Potential risks: No experimental pharmacological intervention will be used in this study. On the contrary, the study aims to enhance recognition of dementia and provide collaborative dementia care management that is recommended to enhance dementia care. Although data will not be gathered from the patient without his or her consent, it is possible that some of the questions related to dementia screening and management asked of the respondents could cause anxiety.

The research personnel will be trained to recognize and minimize this discomfort and patients may discontinue participation at any time. If a respondent becomes anxious or upset, the principal investigator will be notified to intervene. Furthermore, patients who undergo the screening process and or the subsequent diagnostic assessment may end up with a dementia diagnosis. The impact of this diagnosis on their quality of life and care is not known and thus potential harms such as discrimination, loss of independence, or psychological burden may occur. On the other hand recognizing the presence of dementia would lead to receipt of appropriate and valuable treatment both pharmacologically and non-pharmacologically. Such a treatment may decrease the patient's disability resulting from unrecognized or unmanaged dementia and enhance the patients' adherence of medical management of other health conditions. Loss of confidentiality is also a risk in this type of data collection. Our data management and quality assurance technique has proven effective in past trials in maintaining confidentiality, and all study personnel have completed training in Human Subjects Research and HIPAA standards.

Should worrisome conditions such as depression, suicidality, or other concerning clinical conditions be apparent during a research interview, interviewers will follow a scripted protocol to notify the appropriate medical personnel and the PI so that appropriate notification and clinical follow-up is ensured. When such concerns occur for patients while in care management, this will be managed as any other clinical issue would be under usual circumstances through notification of the appropriate primary care provider or emergency personnel depending on the severity of the presentation. Again, the PI and other supporting staff are available to assist if and when this may occur.

Adequacy of protection against risks

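### The harm aim covers PHQ-9 and GAD-7 at 1, 6 and 12 months, but the only planned between-arm analysis is a 1-month ANCOVA that does not refer to the 0.6 and 0.5 equivalence margins

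*Combined protocol and SAP*

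**What the plan says.** - **Aim.** Primary Specific Aim 2 is to "Test the impact of dementia screening on the mood and anxiety symptoms of patient at baseline and 1, 6, and 12 months", and it calls these the main potential harms. Its hypothesis is narrower and directional: "screened subjects will not have higher depression or anxiety at one month post-screening".
- **Data.** Section I lists as outcomes "mood (PHQ-9) and anxiety levels (GAD-7) obtained at baseline, 1, 6, and 12 months"; Section H (Mood and Anxiety Outcomes) agrees.
- **Analysis.** Section I, Secondary Aim 1: "ANCOVA models will be used to compare PHQ-9 and GAD-7 obtained at 1 month between the screening and no screening groups", adjusted for patient characteristics and baseline. It gives no margin, confidence level or rule for concluding no harm. The longitudinal model in the Primary Aim paragraph is specified "using repeated HUI measures as the dependent variables, group, time, interaction between group and time as independent variables"; neither harm scale is mentioned there.
- **Power.** The Statistical Power paragraph says "we will have greater than 95% power to test the equivalence levels in PHQ-9 and GAD-7 at 1 month", with equivalence differences of 0.6 (SD 5.1) and 0.5 (SD 3.2).
- **Disclosure.** In Section E the diagnosis is settled after a first home visit and explained at a second one, 2 to 4 weeks later. No limit is stated for the time from screening to the first visit. Section L (Potential risks) says of a dementia diagnosis that "potential harms such as discrimination, loss of independence, or psychological burden may occur".
- **Label.** The aim is primary in the aims section, but secondary in Section I and in Section K, item 7.

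**The concern.** The trial is meant to weigh the benefits of screening against its harms. The benefit outcome is compared at 12 months and modelled over time. The harm outcomes are compared once, at the earliest visit. Followed as written, the plan yields no between-arm depression or anxiety estimate at 6 or 12 months, although the aim names those visits and the data will exist. The diagnosis is one of the routes to harm that the protocol itself names, and some subjects may learn of theirs after the 1-month interview.

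Separately, the plan does not say which 1-month result would support a no-harm conclusion. The margins appear only in a power sentence. The hypothesis asks whether screened subjects are worse, and equivalence asks whether the arms differ in either direction. Section M has the DSMB review anxiety and depression, but that is safety monitoring and specifies no comparative estimate.

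**Working it through.** **Inputs.** From Section I: 4,000 subjects randomised 1:1, so 2,000 per arm; margins and SDs as above; 10% missing at 12 months, so 1,800 per arm (applied to every visit as an assumption). From Section E (Screening Process): about 100 subjects diagnosed in the screening arm. Assumed: baseline-to-follow-up correlation r, from 0 (unadjusted) to 0.5. The documents give neither r nor an alpha for the equivalence test.

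**1. The plan's power figure.** SE = SD × √(2/n). At 2,000 per arm, PHQ-9: 5.1 × √(2/2000) = 0.1613; GAD-7: 3.2 × √(2/2000) = 0.1012. With a true difference of zero:

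| Rule | Formula | PHQ-9 | GAD-7 |
|---|---|---|---|
| Two one-sided 5% tests (90% CI) | 2Φ(margin/SE − 1.645) − 1 | 96.2% | 99.9% |
| One-sided 2.5% (upper 95% limit) | Φ(margin/SE − 1.96) | 96.1% | 99.9% |
| Two one-sided 2.5% tests (both 95% limits) | 2Φ(margin/SE − 1.96) − 1 | 92.2% | 99.7% |

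The first two rules reproduce the stated figure of over 95%; the third does not for PHQ-9. The power sentence therefore does not settle which rule is meant.

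**2. Does the form of the test matter at 1 month?** With adjustment, SE is multiplied by √(1 − r²).
- PHQ-9, SD 5.1, r = 0.5: 1.96 SE is 0.274 (2,000 per arm) or 0.289 (1,800). The largest non-significant estimate has an upper 95% limit of twice that, 0.547 or 0.577. Both are below 0.6, so a non-significant result would also meet the margin. Against the upper 95% limit this needs r above about 0.32 (2,000) or 0.44 (1,800).
- GAD-7, unadjusted, 2,000 per arm: significant above 1.96 × 0.1012 = 0.198, yet inside the margin up to 0.5 − 0.198 = 0.302. An excess of about 0.20 to 0.30 is thus both significant and within the margin.

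**3. Timing of disclosure.** Take the 1-month interview as day 30 (assumed). A second visit 14 to 28 days after the first always falls by day 30 if the first visit is by day 30 − 28 = 2. It always falls on or after day 30 if the first visit is on day 30 − 14 = 16 or later. The lag to the first visit is not given, so the share told by the interview could be anything from all to none.

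**4. Precision at a later visit.** 95% half-width at 1,800 per arm, from r = 0.5 to unadjusted:
- PHQ-9: 1.96 × 5.1 × √(2/1800) = 0.333 unadjusted; × 0.866 = 0.289.
- GAD-7: 1.96 × 3.2 × √(2/1800) = 0.209 unadjusted; × 0.866 = 0.181.

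All are well inside the margins.

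**5. Dilution.** If only the diagnosed are affected, 100/2,000 = 5% of the arm carries the effect, so whole-arm figures are multiplied by 20:
- The half-widths correspond to an average shift in diagnosed subjects of 5.8 to 6.7 PHQ-9 points or 3.6 to 4.2 GAD-7 points.
- A whole-arm difference equal to the margin needs 0.6 × 20 = 12 or 0.5 × 20 = 10 points.

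**6. Multiplicity.** Using the upper 95% limit at 1,800 per arm with no true difference, one visit meets the PHQ-9 margin with probability 0.942 unadjusted or 0.983 at r = 0.5. The chance that at least one of three visits misses it, for between-visit correlation from 0.7 down to 0 (assumed), is 11.8% to 16.5% unadjusted and 3.9% to 5.1% at r = 0.5.

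**The case against.** The strongest reply is that the confirmatory timing is consistent. The hypothesis is set at one month, and the analysis text, the power paragraph and the time line all follow it. By then every screened subject has been tested and those screening positive have been referred, so 1 month is a reasonable time to look for screening-related distress across the arm. This stands. What is missing is an analysis for the rest of the aim, not a test of the hypothesis.

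A second reply is that ANCOVA supplies the adjusted difference while the power paragraph supplies the equivalence inference, so the two are compatible. That also stands in part: what is absent is the link, the confidence level and the one- or two-sided form.

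Several stronger readings are tempting and not supported:
- *A non-significant ANCOVA would be taken as proof of no harm.* No passage says so, and the power paragraph points the other way.
- *A non-significant PHQ-9 result could conceal an excess beyond the margin.* With the baseline adjustment that the plan specifies, SD 5.1 and r = 0.5, it could not. Disagreement needs a weaker correlation or a larger SD, and it shrinks or disappears under the 90% interval that equally fits the stated power.
- *The 1-month visit precedes disclosure.* It may for some; the documents give no share.
- *The plan would move the outcome analysis off the raw scale.* The provision to "use alternative approaches such as transformation or nonparametric methods in cases of violation to the normal distribution assumption" directly follows the baseline-comparability tests and is not stated for the outcome models.
- *Analysing later visits would reveal harm in diagnosed subjects.* Dilution makes that unlikely unless the harm is large.

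**Conclusion.** The point holds as a mismatch between aim and analysis. Two of the three post-baseline visits named in the harm aim have no planned between-arm comparison of PHQ-9 or GAD-7, and the 1-month comparison is not tied to the margins for which the trial claims power. The aim's directional form, the power paragraph's equivalence form and the primary or secondary label also need reconciling. The stated power is sound.

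The practical effect of the test form is small. It is mainly a GAD-7 excess of about 0.20 to 0.30 (unadjusted, 2,000 per arm, 95% interval) that would be significant yet within the margin, which errs toward declaring harm. These sizes rest on the plan's SDs, on 10% missing at each visit where 1,800 per arm is used, and on r between 0 and 0.5. The absence of 6- and 12-month analyses rests on the text alone.

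**What to change.** 1. Fit the mixed-model form already planned for HUI to PHQ-9 and GAD-7. Report adjusted between-arm differences with 95% confidence intervals at 1, 6 and 12 months. Keep 1 month as the hypothesis test, do not require all three visits to pass, and limit any no-harm statement to the visits that support it.
2. In the Secondary Aim 1 paragraph, base the 1-month conclusion on the confidence interval for the adjusted raw-scale mean difference against 0.6 and 0.5. State the level and form: either the upper limit of a 95% interval, which suits the directional hypothesis, or a 90% interval for two one-sided 5% tests. Make the aim, the analysis and the power paragraph agree. Any transformed or rank analysis of these outcomes should be a sensitivity analysis, because the margins are in raw points.
3. Use one label, primary or secondary, in the aims, Section I and Section K.
4. Add a descriptive summary of PHQ-9 and GAD-7 change in screen-positive and diagnosed subjects, stated to have no randomised comparator.

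The cost is SAP wording and a little more model output; no new data are needed. The drawbacks are some multiplicity across visits, which is why no three-visit gate is proposed, and the dilution shown above. The report should say that the later estimates describe the effect of the screening policy and cannot rule out sizeable harm among those diagnosed.
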